5.5. Screening Procedures

Written informed consent to enter into the trial must be obtained from participants, after explanation of the aims, methods, benefits and potential hazards of the trial and **BEFORE** any trial-specific procedures are performed or any blood is taken for the trial. The only procedures that may be performed in advance of written informed consent being obtained are those that would be performed on all patients in the same situation as usual standard of care.

5.6. Informed Consent Procedure

Written informed consent will be taken from each subject by an investigator or delegate following appropriate explanation of the aims, methods, possible benefits and risks of the study. The investigator or designee will explain that the participants are under no obligation to enter the trial and that they can withdraw at any time during the trial, without having to give a reason, and without their clinical care being affected. No clinical trial procedure will be conducted prior to taking consent from the participant.

If new safety information results in significant changes in the risk/benefit assessment, the participant information sheet and consent form will be reviewed and updated if necessary, and participants will be re-consented as appropriate.

5.6.1. Informed Consent for Optic Neuritis, AMD & Glaucoma Patients

Eligible patients for the trial in these affected groups will be approached by members of their usual care team who will present the study to them and provide them with the patient information sheet (PIS) to take home.

Individuals will be given sufficient time to allow them to decide whether or not they would like to participate. Patients will have it explained to them that they are under no obligation to enter the trial and that they can withdraw at any time during the trial, without having to give a reason. Prior to documenting consent in writing, Investigators will ensure all aspects of the study have been fully understood and that all questions have been answered satisfactorily.

No clinical trial procedures will be conducted prior to having obtained fully informed consent in writing.

A copy of the signed Informed Consent form will be given to the participant. The original signed form will be retained at the study site in the site file and a copy placed in the medical notes.

5.6.2. Informed Consent for Down's Syndrome Participants

For participants in this affected group the consent process will be managed as follows:

A domiciliary visit will be arranged for each potential Down's syndrome participant. The trial will be discussed with the DS participant and this will be facilitated by the use of easy read information sheets. The trial team fully expect that all DS participants who will take part in the DARC II trial will be capable of forming an opinion, explicitly expressing their wishes in regards to participation, and signing an easy read consent form. The opinion of the DS participant will be fully considered and respected. If a DS participant is not considered to have capacity to consent they will be excluded from the DARC II trial. If the potential participant is found to lack the capacity to form an opinion and to consent or withdraw from this study they will not be included in this research.

To be considered to have capacity to consent the DS participant will need to meet the following 5 criteria:

1. The subject has had an interview with the Principal Investigator for Down's syndrome (xxxxxxx) in which they have been given the opportunity to understand the objectives, risks and inconveniences of the trial and the conditions under which it is to be conducted.
2. The subject has been informed of their right to withdraw from the trial at any time.
3. The subject has given their informed consent to taking part in the trial.
4. The subject may, without being subject to any resulting detriment, withdraw from the clinical trial at any time by revoking their informed consent.
5. The subject has been provided with a contact point where they may obtain further information about the trial.

Down's syndrome patients that are considered to have a significant learning disability or dementia will be excluded from participating in the DARC II trial. All potential Down's syndrome participants will previously have completed Cognitive Ability Assessments and Dementia Diagnosis Interviews. Down's syndrome participants will need to demonstrate an IQ of at least XX at their last Cognitive Ability Assessment (which must have been in the previous 3 months) in order to be considered to have sufficient cognitive ability to have capacity to consent. And Down's syndrome participants with an IQ of below XX will be considered to have a significant learning disability and be excluded from the trial. The parent/carer of Down's syndrome participants will also need to have completed a Dementia Diagnosis Interview (within the last 3 months) and there must be no indication or diagnosis of dementia for the potential Down's syndrome participant. If the Down's syndrome participant has a diagnosis of dementia or in the experience of the Down's syndrome Principal Investigator has experienced significant cognitive decline they will be excluded.

Down's syndrome participants will have all the trial procedures explained to them again on the day of the intervention and before and trial specific procedures take place. If the Down's syndrome participant gives any indication that they do not wish to proceed with the trial, then they will be withdrawn immediately.

The inclusion of DS participants has been carefully considered by the trial team. The trial interventions have been designed to minimise pain, discomfort and fear for the all participants. The consent process will be conducted by xxx (the PI for the DS cohort) who is already known to all of the potential DS participants.

We will begin the recruitment of the DS participants last. The first Down's syndrome participant will not receive the intervention until a minimum of 20 participants from the other study groups (Glaucoma, AMD, Optic Neuritis and healthy volunteers) have received the intervention and completed the 30 day follow up for adverse events. At this point the IDMC will review the available safety data and make a recommendation to the TSC regarding whether recruitment of Down's syndrome participants can commence. The TSC will ultimately make the decision regarding the commencement of recruitment of Down's syndrome participants (section xxx).

Despite the study drug being an investigational medicinal product, the intervention is considered low risk. The trial requires a home visit, a hospital visit, and a follow up telephone call so the burden for potential participants is minimal. No serious adverse events were observed in the phase I clinical trial of DARC. It is unlikely there will be any direct benefit to participants in the DARC II trial. However it is entirely possible that the onset of dementia may be detected earlier through their participation in the DARC II trial. DS patients will be required to complete Cognitive Ability Assessments, and their parent/carer will complete a Dementia Diagnosis Interview. If onset of dementia is detected this will be fed back to the DS participant and their parent/carer appropriately. The potential for the DARC in

the DS population is huge, and the trial team strongly believe that DS participants should be given the opportunity to participate in the trial.

5.6.3. Informed Consent for Healthy Volunteers

Healthy Volunteers will be recruited by way of advertisements and so may contact the trial team directly expressing interest in being recruited. Healthy volunteers will be provided with the Patient Information Sheet for healthy volunteers prior to asking for their consent.

5.6.4. Informed Consent for Optional Exploratory fNIRS

Functional near-infrared spectroscopy will be offered as an optional procedure to participants who are bald, or with short (less than 3cm), fair (unpigmented) hair. The informed consent form will specifically collect consent for the optional fNIRS assessment.

6. Interventions

6.1. Description of intervention

The DARC compound or ANX776 consists of Annexin V (AnxV), covalently bound to an infrared fluorescent dye molecule called Dye-776 (DY-776). The AnxV variant used in this project is commonly known as Anx-128 and differs from the wild type by two single amino acid mutations. The addition of an exposed thiol group at the N-terminus affords increased conjugation efficiency for the molecular tag. DY-776 is a proprietary dye produced by the company Dyomics and is available for conjugation in its maleimide form, providing 1:1 dye:protein ratio. ANX776 is a diagnostic agent and therefore a subject will only receive a single dose of the IMP.

The retinal imaging procedure will be conducted in both eyes after pharmacological mydriasis (1% tropicamide and 2.5% phenylephrine). In preparation for the administration of the IMP the participant will be cannulated, and seated comfortably in chair while resting their chin on a chin-rest and facing the retinal camera. When the individual is ready, a member of clinical staff qualified to administer intravenous injections will inject ANX776. Following the injection retinal images will be taken at predetermined time intervals, as per protocol. During this time, participants will be closely monitored for safety by the study doctor. All aspects of the intervention will be identical for all study groups. fNIR spectroscopy will be performed as an optional procedure using an optical cap with NIRS optodes in patients defined in section xxx. This 'cap' will be placed on the participant's head and secured beneath the chin using a soft Velcro strap. During the time a participant is having their retinal imaging done (chin in chinrest, and focusing on the camera), the signal reading generated by the fNIRS will be recorded by the device. Hence there will be no extra burden to the participant.

6.2. Treatment Schedule

The ANX776 IMP will be given as a single intravenous bolus dose (0.4mg) to the trial participants. This is the optimal dose as deemed by the results of the phase I trial of DARC. The injection will be given through a cannula inserted into the participants arm. The cannula will be removed immediately after the injection.

6.3. Dispensing

The ANX776 IMP will be prescribed by the study Investigator with suitable prescribing qualifications. It can be administered by any member of clinical staff qualified to administer intra venous infusions.

6.4. Accountability

ANX776 is classed as an IMP and therefore will be accounted for in line with MHRA regulations. The amount of ANX776 administered to each patient will be recorded in the CRF, including recording the

batch number. The unused IMP will be disposed of as per local standard procedures. IMP shipping instructions for the site will be in the Summary of Drug Arrangements.

Biotec Services International will inform the site contact listed on the drug order form by e-mail when a shipment is sent. On receipt pharmacy will segregate and store the drug appropriately and protected from light at -20°C immediately, and log receipt of each batch of ANX776 on the Accountability Log in a timely manner. Following delivery of ANX776 pharmacy will inspect and verify the contents and conditions of the shipment. An acknowledgement of receipt of ANX776 will be included with the received vials. Usual procedures for monitoring of temperature and transport conditions of the IMP will apply and will be documented on the IMP shipping form. Upon receipt of the IMP, the site pharmacy will confirm receipt of the IMPs by posting/faxing back the accompanying shipping form to the supplier and copies retained at trial sites file. Pharmacy must file a copy of the acknowledgement receipt in the Pharmacy Site File.

If the vials containing ANX776 arrive damaged, pharmacy must quarantine the product, and contact the Sponsor Representative. The Sponsor will arrange for replacement stock to be sent if required. All correspondence relating to delivery problems or any other problem with respect to ANX776 must also be documented and filed in the Pharmacy Site File. If the ANX776 has not arrived by the expected date and time, pharmacy must contact the Trial Management Team in the first instance.

In cases where the IMP is damaged or not stored correctly, this will warrant an urgent notification to the manufacturer who will advise the site and sponsor as to whether a replacement needs to be arranged. The sponsor will be responsible for liaising with Dompé Farmaceutici S.p.A and Biotec Services International (where vials will be labelled and released to the Clinic) for dispatching replacement IMPs to sites. Site pharmacy will be responsible for logging receipt of the IMPs on the site accountability log within the site pharmacy file. Site pharmacy will be responsible for storing the IMP in line with storage requirements as set out in the IMPD (briefly, at -20°C and protected from light, prior to dispensing each vial, thawing at 2-8°C, in the dark, without agitation will be required). Site pharmacy will monitor temperature of IMP storage and report to the sponsor any temperature excursions that have occurred. Details of reporting temperature excursion are in the Summary of drug arrangements. Full IMP accountability will be conducted during the trial. All IMP dispensed by pharmacy will be logged on the site accountability log within the site pharmacy file.

Once the IMP is dispensed, it will be stored at site pharmacy at 2-8°C, protected from light. The storage temperature will be monitored by a thermograph, with a Temperature log kept as standard procedure. The IMP will be warmed to room temperature in the IMP administration room where it will be protected from light prior to IV administration. The IMP will be administered to subjects within 24 hours of dispensing and the administration of the IMP will be documented in the source data and CRF. All used/unused IMP vials will be returned to site pharmacy, to be then updated in the drug accountability log in the pharmacy site file. Drug destruction will be conducted, once agreed with the sponsor and in accordance to local practice, and this will be documented in the drug destruction log in the hospital pharmacy file.

6.5. Source of IMPs including placebo

The IMP will be packaged, labelled and QP released for clinical trial use by an MIA(IMP) holder.

The IMP is being manufactured by:

Dompé Farmaceutici spa - [name].

Drug substance release tests:

Dompé Farmaceutici spa - [name].

Drug product characterisation release tests:

Dompé Farmaceutici spa - [name].

Drug Product manufacture and release tests (Sterility, Bioburden, Subvisible Particles):
Patheon UK Limited - [name].

The IMP is being packaged, labelled and released to the clinic by:
Biotec Services International – [name].

The sourcing of IMPs is discussed in the summary of drug arrangements.
IMP storage, dispensing and relevant administrative activities will be based at the Western Eye Hospital's pharmacy that has compliant freezer and fridge facilities as well as a clinical trials dedicated technician.

6.6. Compliance and Adherence

It is not expected that there will be any problems with compliance as ANX776 will be administered by trial clinicians in charge of the patients care.

Any interruptions or dose modifications will be expected to be recorded in the patient's hospital notes and on the trial CRFs.

6.7. Concomitant Care

All medication and treatment will be continued as normal and will be recorded in the CRF.
Proxymetacaine hydrochloride 0.5% and Fluorescein Sodium 1% eye drops will be used for intraocular pressure assessment. Tropicamide 1% and phenylephrine 2.5% eye drops will be used to induce pharmacological mydriasis during visit days. Any concomitant glaucoma medication that the subject is receiving will be permitted. There are no comparator products or placebos.

6.8. Overdose of Trial Medication

All study groups will receive the same intervention, consisting of a single intravenous injection of 0.4mg of ANX776; there will be no dose escalation. Injection will be followed by assessment of retinal cell apoptosis performed using diagnostic retinal imaging.

The DARC Phase I evaluation of safety and tolerability has shown ANX776 to be well tolerated at all trialled doses (0.1mg, 0.2mg, 0.4mg and 0.5mg) with only minor and unrelated adverse events having been observed. In adherence with the protocol, all participants will be closely monitored for continued evaluation of safety and tolerability.

6.9. Protocol Treatment Discontinuation

In consenting to the trial, participants are consenting to trial treatments, trial follow-up and data collection. However, an individual participant may stop treatment early or be stopped early for any of the following reasons:

- Unacceptable treatment toxicity or adverse event
- Inter-current illness that prevents further treatment
- Any change in the participant's condition that in the clinician's opinion justifies the discontinuation of treatment
- Withdrawal of consent for treatment by the participant

As participation in the trial is entirely voluntary, the participant may choose to discontinue trial treatment at any time without penalty or loss of benefits to which they would otherwise be entitled. Although not obliged to give a reason for discontinuing their trial treatment, a reasonable effort should be made to establish this reason, whilst remaining fully respectful of the participant's rights. Participants who discontinue protocol treatment, for any of the above reasons, should remain in the trial for the purpose of follow up and data analysis.

6.10. Accountability procedures for investigational products

ANX776 will only be used for trial subjects.

All intravenous injections will be prepared under GMP regulations and identical dosages of the tracer will be given to all subjects according to the study group.

The setting up of protocol procedures and IMP pathway logistics will be done by the dedicated Pharmacy Clinical Trials Team at St Mary’s Hospital. The on-site pharmacy based at the Western Eye Hospital will be in charge of storage, dispensing and keeping related records.

6.11. Contingency planning for abnormal findings

If the DARC II trial procedures result in any abnormal findings, these findings will be fed back to the participant (and their parent/carer for Down’s syndrome participants) in a timely and appropriate manner by the study doctor. The trial team will ensure that the patients GP is informed, and that the participant is directed to appropriate care services.

7. Outcomes

7.1. Primary Outcomes

The primary outcome is the efficacy of the intervention ascertained by the DARC Count, which is the number of apoptosing retinal cells visualised 4 hours after the ANX776 injection.

7.2. Secondary Outcomes

Safety is defined as absence of an adverse event of grade 3 or above in the following study groups:

- 20 participants with AMD,
- 20 participants presenting with acute vision loss from optic neuritis,
- 20 participants with Down’s syndrome,
- 20 participants with glaucoma,
- 40 healthy volunteers.

Safety will be measured by adverse events following the Common Terminology Criteria for Adverse Events (CTCAE) scale.

In addition, in a subset of participants, an exploratory secondary objective is to assess if the ANX776 signal is detected in the brain using fNIR spectroscopy.

8. Participant Timeline

Figure 1: Participant Timeline

Type of procedure	Procedure	Study Visit
Qualification Procedures	Informed Consent	X
	Medical and Ophthalmic Histories	X
	Prior & Concomitant Medications/Procedures	X
	Demographic data	X
	Cognitive Ability Assessments	X ⁸
	Dementia Diagnosis Interview	X ⁹
	Physical Examination	X
	Vital Signs	X

	Visual Acuity	X⁴
	Slit-Lamp Bio-microscopy (incl. Corneal Pachymetry and IOP)	X⁴
	Visual Field (HVF)	X, X, X^{1,3,4}
	Fundus Exam (Post-Pupil Dilation)	X⁴
	Baseline fundus autofluorescence (IR)*	X⁴
	Optical Coherence Tomography (OCT)	X, X, X^{1,3,5}
	Heidelberg Retinal Tomography (HRT)	X, X, X^{1,3,4}
	Childbearing potential / pregnancy test	X
	Eligibility Confirmed	X
Intervention Procedures	Intravenous Administration of Study Drug - ANX776	X⁶
	DARC assessment by cSLO Retinal Imaging*	X, X, X, X^{2,6}
	Adverse Medical Event Query	X⁶
Post intervention	Safety follow up telephone call	X⁷

1. Up to 2 reliable historical tests, obtained no more than 24 months prior to the qualification / pre-intervention visit, can be used as part of this qualification assessment of Glaucoma, healthy volunteers, AMD, Downs syndrome and Optic Neuritis subjects.
 2. During injection, 15 min, 2 hours and 4 hours post injection.
 3. Confirmation of historical findings for Glaucoma, Optic neuritis and AMD participants.
 4. Down's participants are exempted from this test.
 5. For Down's participants, historical data will be used.
 6. Can be conducted up to 12 weeks from confirmation of eligibility.
 7. 30 days after DARC Intervention +/- 1 week
 8. Down's participants only
 9. Down's participants' parent /carer only
- * In a subset of participants this will be done in conjunction with fNIR spectroscopy (as described in section xxx)

9. Procedures

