6.6. Compliance and Adherence	14
6.7. Concomitant Care	14
6.8. Overdose of Trial Medication	14
6.9. Protocol Treatment Discontinuation	14

6.10.	Accountability procedures for investigational products	14
6.11.	Contingency planning for abnormal findings	15
7.	Outcomes	15
7.1.	Primary Outcomes	15
7.2.	Secondary Outcomes	15
8.	Participant Timeline	15
9.	Procedures	16
9.1.	Qualification/ pre-intervention assessment	16
9.2.	Treatment procedures	17
9.3.	Intervention (within 12 weeks of Qualification)	17
9.4.	Safety follow up telephone call (30 days after intervention)	17
9.5.	Early Stopping of Follow-up	17
9.6.	Loss to Follow-up	17
9.7.	Trial Closure	17
9.8.	Data queries	18
10.	Ethics and Dissemination	18
10.1.	Research Ethics Approval	18
10.2.	Competent Authority Approvals	18
10.3.	Other Approvals	18
10.4.	Protocol Amendments	19
10.5.	Consent or Assent	19
10.6.	Confidentiality	19
10.7.	Declaration of Interests	20
10.8.	Indemnity	20
10.9.	Finance	20
10.10.	Archiving	20
10.11.	Access to Data	20
10.12.	Ancillary and Post-trial Care	20
10.13.	Publication Policy	21
10.13.1.	Trial Results	21
10.13.2.	Authorship	21
10.13.3.	Reproducible Research	21

1. Trial design

This Phase II trial will be a single-centre, open-label, cross-sectional study in patients diagnosed with Glaucoma, Age-related Macular Degeneration, Optic Neuritis, individuals with Down's syndrome, and healthy volunteers.

A sample size of 120 subjects is planned in 5 study groups:

[figure not shown]
- Healthy volunteers: 40 subjects
- Glaucoma: 20 subjects
- Age-related Macular Degeneration: 20 subjects
- Optic Neuritis: 20 subjects
- Down's Syndrome: 20 subjects

The Down's syndrome participants will be recruited and receive the intervention last.

Subjects in each study group will receive the same amount of ANX776 and each individual subject will receive 1 single intravenous injection. All subjects will be enrolled in accordance with the inclusion and exclusion criteria outlined in Section xxx and via the recruitment strategy in Section xxx.

DARC imaging will be performed in all participants to assess retinal cell apoptosis. However, in a subset of participants (as described in section xxx), fNIR spectroscopy will be performed simultaneously as an optional procedure.

2. Trial Diagram

3. Abbreviations

AE	Adverse Event
Anx-A5	Annexin A5
AR	Adverse Reaction
AMD	Age-related Macular Degeneration
CI	Chief Investigator
CRF	Case Report Form

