9.4. Safety follow up telephone call (30 days after intervention)

The site will conduct a safety follow up via telephone call to the subject/carer 30 days after IMP administration, to check for any symptoms and/or adverse events.

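### Section 7.2 equates safety with zero grade 3+ adverse events in groups of 20 to 40, and names no relatedness, observation period, or per-group or pooled basis

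*Protocol*

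**What the plan says.** Protocol section 7.2 (Secondary Outcomes) sets the safety outcome: "Safety is defined as absence of an adverse event of grade 3 or above in the following study groups". The list that follows gives 20 participants each with AMD, optic neuritis, Down's syndrome and glaucoma, and "40 healthy volunteers". It adds: "Safety will be measured by adverse events following the Common Terminology Criteria for Adverse Events (CTCAE) scale". CTCAE grades severity, and the section says nothing on relatedness, on how long participants are observed, or on whether the definition is applied group by group or to all participants together.

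The follow-up period has to be gathered from other places:

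- Section 8, Figure 1, footnote 7 times the safety call at "30 days after DARC Intervention +/- 1 week".
- Section 9.4 gives no tolerance: "The site will conduct a safety follow up via telephone call to the subject/carer 30 days after IMP administration".
- Section 5.6.2 holds back the first Down's syndrome injection until at least 20 participants from the other groups "have received the intervention and completed the 30 day follow up for adverse events". The IDMC then reviews the available safety data and the TSC decides.

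Section 10.12 plans no further visits, so the call is the only scheduled contact after discharge.

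**The concern.** A definition by absence gives a yes/no answer that groups of this size cannot carry, and it can mislead in two directions. A group with no event would meet the definition even though a clinically important rate has not been ruled out. A group with one grade 3 event that has nothing to do with the injection would fail it.

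The protocol does recognise relatedness elsewhere. Its abbreviation list separates adverse events from adverse reactions, and section 6.8 describes the phase I events as unrelated. Section 7.2 does not carry the distinction over. Section 9.2 calls the trial a safety study, so how the safety result is worded matters.

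The missing period adds a smaller problem. If the call is made on day 23, no scheduled enquiry covers the last week of the 30 days. The protocol does not say whether such a participant counts as having completed follow-up for the Down's syndrome review.

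**Working it through.** **Inputs from the protocol.** The group sizes are 20, 20, 20, 20 and 40 (section 7.2). They reproduce the planned total: 40 + 4 × 20 = 120 (section 1: "A sample size of 120 subjects is planned in 5 study groups"). The protocol gives no expected event rate, tolerated rate or precision target, so the event rates below are assumptions and are shown as ranges.

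**1. What zero events would exclude.** The two-sided exact 95% (Clopper–Pearson) upper limit with no events is 1 − 0.025^(1/n). The one-sided limit is 1 − 0.05^(1/n).

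| n | Two-sided | One-sided |
|---|---|---|
| 20 | 16.8% | 13.9% |
| 40 | 8.8% | 7.2% |
| 120 | 3.0% | 2.5% |

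**2. How often the definition is met at a given true rate.** P(no event) = (1 − p)^n.

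| True rate p | n = 20 | n = 40 |
|---|---|---|
| 2% | 66.8% | 44.6% |
| 5% | 35.8% | 12.9% |
| 10% | 12.2% | 1.5% |

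For example, 0.95^20 = 0.358, so at a true rate of 5% a group of 20 meets the definition more than one time in three.

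**3. How often unrelated events alone defeat it.** P(at least one) = 1 − (1 − p)^n, where p is an assumed 30-day risk of an unrelated grade 3+ event.

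| Assumed p | n = 20 | n = 40 | n = 120 |
|---|---|---|---|
| 0.5% | 9.5% | 18.2% | 45% |
| 1% | 18.2% | 33.1% | 70% |
| 2% | 33.2% | 55% | 91% |

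The last column applies only if the definition is read over all 120 participants, or as the chance that at least one of the five groups fails. Section 7.2 does not say which basis is meant, and at p = 1% the choice moves the figure from 18% to 70%.

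**4. What an estimate would show instead.** One event in 20 is 5% (exact 95% interval 0.1% to 24.9%). One event in 40 is 2.5% (0.1% to 13.2%). Either result is informative, while the definition as written records only that safety was not met.

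**5. The call window.** Day 30 ± 7 gives day 23 to day 37. A day-23 call leaves 7/30 = 23% of the period without scheduled enquiry. Assuming a constant hazard, P(no event by day d, n = 20) = (1 − p30)^(20 × d/30).

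| 30-day risk p30 | Day 23 | Day 30 | Day 37 |
|---|---|---|---|
| 1% | 85.7% | 81.8% | 78.0% |
| 5% | 45.5% | 35.8% | 28.2% |

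The window moves the result by about 4 to 10 percentage points, and it can move it either way. The small-group problem in steps 1 and 2 is the same with every call exactly on day 30.

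**The case against.** The strongest reply is that section 7.2 only names an outcome. It can be read as a participant-level endpoint (free of grade 3+ events) tabulated by group, with estimates and intervals left to an analysis plan that is not shown here. Part of this stands: interval methods and table layouts normally belong in that plan. But the protocol goes further than naming a measure, because it states what safety is. An analysis plan that reported rates in place of absence would be changing the outcome definition.

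It can also be said that counting events whatever their cause is a reasonable, conservative choice in an uncontrolled open-label trial, where attribution is subjective. That is fair, and it is why both counts should be reported. The protocol does not say that all causes count. That reading follows from the missing qualifier, and the text shown has no adverse-event reporting section that could settle it.

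The background rates are assumed. Section 5.6.2 reports no serious events in phase I, section 6.8 only slight ones, and section 5.2.3.1 excludes severe or unstable systemic disease. The lower end of the range may therefore be the more apt.

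A reader might infer three stronger things that the protocol does not support:

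- **That zero events carry almost no information.** The limits in step 1 show otherwise: 0/20 excludes rates above about 17%, and 0/120 excludes rates above about 3%.
- **That a failed definition stops the trial or blocks the Down's syndrome group.** The only safety gate shown is the IDMC and TSC review in section 5.6.2, and it is not tied to zero events.
- **That the call window loses late events as a matter of course.** It is symmetric, and a loss needs both an early call and an event in the final week. Footnote 7 can also be read as an ordinary tolerance around the day named in section 9.4. What remains open is its fit with a completed 30-day follow-up in section 5.6.2.

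**Conclusion.** The point holds for the definition itself. Section 7.2 equates safety with the absence of grade 3+ events and fixes neither relatedness, nor period, nor per-group or pooled basis. At the planned sizes, absence leaves rates of up to 16.8% (n = 20), 8.8% (n = 40) and 3.0% (n = 120) unexcluded. These limits need no assumption beyond independent participants and full enrolment and follow-up. The chance that one unrelated event defeats the definition in a group of 20 is 9.5% to 33.2%. That figure rests wholly on an assumed 30-day background rate of 0.5% to 2%, and on reading the missing qualifier as including unrelated events.

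The consequence is a safety conclusion that the data could not support or could lose by chance. No stopping rule is affected. The difference in call timing is secondary. It is worth settling because the review before Down's syndrome participants are injected relies on follow-up being complete.

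**What to change.** In section 7.2, replace the definition by absence with: the number and proportion of injected participants with at least one CTCAE grade 3 or higher adverse event, and with at least one such event judged related to ANX776, over a stated period after injection, by group and pooled over all injected participants, each with an exact 95% interval. The upper limits that zero events would give (16.8%, 8.8% and 3.0%) can be stated alongside, so that a clean result is not over-read.

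Separately, reconcile section 8 footnote 7, section 9.4 and section 5.6.2, so that follow-up counted as complete covers the full 30 days they name. How the call is scheduled to achieve this is for the trial team.

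The cost is an amendment to wording, with no extra participants or procedures in 7.2. Relatedness must be recorded for each grade 3+ event. The safety statement becomes visibly less strong, and reconciling the call timing may reduce the site's flexibility.
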